b. Breach of confidentiality: The likelihood of loss of privacy or confidentiality is rare and its impact on participants is likely to be minimal. Risks to privacy and confidentiality associated with this study will be described in the consent form along with our procedures to minimize this risk. Participant confidentiality will be maintained through a number of strategies. Each participant will be assigned a unique study identification number. The only individuals who will have access to participants' identifiers will be the PD, assessors, mindfulness instructors, and health educators. Mindfulness instructors and health educators must have access to participant identifiers in order to call the participants for their weekly sessions. Assessors will have access to participant identifiers in order to call the participants for their monthly pill counts. Assessors, mindfulness instructors, and health educators are all trained and experienced in following research protocols and participant confidentiality. Audio recordings of mindfulness and health education sessions will be reviewed promptly to ensure treatment fidelity and then destroyed. Checklists and paper records of the treatment fidelity review will not include identifying information but will be stored and handled using the same methods as with other paper data. Audio recordings of interviews will be summarized without participant identifiers and then destroyed following analysis.

Protection of study data will be assured by the use of locked files and password-protected computer databases with access available only to the study personnel. Biospecimens will be labeled only with the collection date and an anonymous numerical code; no identifiable patient information will be present on the samples. The PD will be responsible for collecting, handling and bringing the samples to the designated lab for analysis; no other personnel will have access to these samples.

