7.6. Blinding

This is a phase 2 pilot study testing the feasibility of a behavioral intervention; participants will not be blinded.

Blinded personnel:

- Principal Investigators and all Co-Investigators
- Data management and data analysis personnel
- MT and AC instructors will be blinded to the study outcomes.

Non-blinded personnel:

- Project Director. Blinding the PD would be impractical given that she will be randomizing the patients to either condition. The impact of un-blinding the PD will be minimal because study

surveys are completed electronically by participants and the PD will NOT be involved in data analysis.

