8. STUDY ASSESSMENTS

Overview

Table 8.2 provides the schedule of study assessments for this pilot RCT. All assessments will be conducted in-person. The PD will be responsible for data collection; see section 7.6 for blinding consideration. Because not all participants can be reached for assessments on their due date, windows have been established to determine when to record a protocol violation or consider assessments missing (Table 8.1).

Table 8.1

Assessment	Window
Baseline	Within 60 days from screening visit
Post-Intervention	Within 2 weeks of final intervention session
Follow-up	12 weeks (+/- 2) after completing final intervention session

All visits will be conducted at the Immunology Center (described earlier).

Table 8.2 Schedule of Study Assessments

Assessment	S	BL	At each session	Post	FU
Screening					
HIV infection status	X				
ART adherence	X				
Viral load	X				
Psychological distress	X				
Sexual risk behavior (past 3 months)	X				
Prior mind-body training	X				
Hearing impairment	X				
Suicidal ideation	X				
Telephone Access	X				
Literacy	X				
Feasibility and Acceptability					
n of screened individuals		X			
n eligible		X			
n enrolled		X			
n refusing to participate		X			
Reasons for refusing participation		X			
n of dropouts and lost to follow-up			X	X	X
Reason(s) for dropping out			X	X	X
Sessions attendance (both conditions)			X		
Individual home practice (both conditions)			X	X	X
Acceptability Survey/ Satisfaction scale				X	X
Qualitative Interview				X	X
Efficacy					

ART adherence: self-reported measure		X		X	X
ART adherence: objective measure (unannounced pill count)		X*		X	X
Viral load (ART adherence biomarker)		X		X	X
Sexual risk: Self-report		X		X	X
STI (sexual risk biomarker)		X			X
Mediators					
Mindfulness		X		X	X
Depression		X		x	X
Anxiety		X		X	X
Perceived stress		X		x	X
Impulsivity		X		x	x
Moderators and Descriptors					
Demographic characteristics		X			
Perceived physical health		X		X	X
Medical history; medications		X			X
Social support		X			
Sleep		X		X	X
Alcohol use		X		X	X
Other Drug Use		X		X	X
Smoking		X		X	X
Nutrition/Eating		X		X	X
Food Security		X		X	X

S = screening; BL = baseline; post = post-intervention; FU = follow-up. * Scheduled within one week of the baseline.

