13.3 Participant Confidentiality

Protection of Participant Privacy: All phone contacts with the participants will take place in a private, locked office and will be conducted by the PD who has been trained and certified in the protection of human subjects in research trials and HIPAA requirements according to TMH policies. Individuals who are interested in the study will provide Contact Information (e.g., name, address, phone, email) and will be scheduled for a screening visit (screening visit 1) to learn more about the study requirements and procedures, and to sign written informed consent as approved by TMH Institutional Review Board (IRB).

In addition, because of the potentially sensitive nature of the data we are collecting, we will apply for a **Certificate of Confidentiality** for this study to ensure that participants' data cannot be subpoenaed with a court order. We have successfully obtained Certificates of Confidentiality for other, similar research projects.

Because some of the qualitative assessments involve participation in focus groups with multiple participants, it is impossible to guarantee privacy of information that is shared in a group format. However, at the beginning of each focus group, a statement will be read to participants regarding maintaining the privacy of information shared in the group. In addition, participants will be reminded of these instructions and to respect each other's privacy and not repeat information shared with the group outside of the study setting at the start of each focus group.

Data Safety

- Participants will be identified with a randomly generated identification code unique to the participant and all personal identifiers will be removed from the study questionnaires and from datasets. Electronic communication with outside collaborators will involve only unidentifiable information. AE reports and annual summaries will not include participant-identifiable material.
- Data collected for screening (i.e. reasons for ineligibility and refusal) and tracking reasons (Filemaker data base) that contain identifiers will be stored into a password-protected server separate from other study data and will be destroyed at study completion. This Filemaker database is password accessible only to the PD, the data systems analyst, and the PI.

- Signed consent forms will be stored in locked filing cabinets separate from all other study data.

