"A pill counter will call you several times during the study to talk to you for the study. The call will be done on the phone while you are home. On the phone calls, the pill counter will ask you to count your medications and tell her how many you have received and what you have left. It is very important we receive accurate information."

Prior to beginning the practice pill count, review the sample pharmacy label with the patient. With the Consultant's assistance, the TMH pill counter will highlight the pertinent information that will be used each month.

Run through a practice pill count using the pills that have been brought in for the baseline assessment.

BE SURE TO EMPHASIZE THE IMPORTANCE OF HAVING ALL MEDICATIONS OUT FOR THE PHONE CALL.

The Pill Counter will run through 3 sample question to demonstrate each type of response. Mention that the caller will also ask some questions about how the participant has been feeling and related issues.

Phone Assessment Training

1. Review the reason for the medication assessment: to learn how people are using their medications so that we can develop better health programs.
2. Provide Health and Assessment Kit.

Contents:

The Pill Tray
Pill Knife
Hand Wipes

3. Explain the pill count protocol. Use the Pill Counting Demo Kit to demonstrate how to count pills.

Mindfulness Training for PLWH

4. Practice a pill count with the Interviewer present. Pour the pills onto the pill tray. Instruct the participant to count their pills out loud by using the pill knife and sliding the pills into the valley of the pill tray. After all of the pills are counted have the participant put the pills back in the medication bottle and count the pills a second time. If the participant does not have medications to count, use the candy (Skittle, Tic Tacs, etc.).
5. Review protocol – answer questions – trouble shoot – problem solve

The Intake Interview is completed....participant given...

Copy of consent form
Take Home Kit
Incentive Payment

Phone Assessments and Pill Count

Time 0 Phone Assessment

Ideally participants are called within 3 days of Initial Intake for their Time 0 phone call.

Materials Needed for Phone Assessments

Previous Call Information Sheet

Assessment Form

Phone Tracking Sheet-(log of participants contacted with their participant ID)

Timing of interviews

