- appears severely distressed during any in-person session (i.e., screening, baseline, or follow-up; as determined by recruiter judgment), or
- reports suicidal thoughts at any time to PD or Instructor, initiate a “distress check” to assess suicidality. This check must be conducted in a sensitive and caring way. For example, you can say to the participant the following: *“I would like to check in with you about how this experience was for you. I asked a lot of questions, and want to check in to ask how are you doing?”*

If participant says he/she is okay and does not meet any of the above criteria for enacting the suicide safety protocol, no further intervention will be taken.

However, if participant says she/he is upset, then the PD or Instructor will say: *“It is not uncommon for people to feel upset or emotional after answering questions like this (or, talking about experiences like this). We do ask many personal questions. It is also not uncommon for people to have thoughts of hurting themselves. Have you had thoughts of actually hurting yourself?”*

If participant has not had any thoughts of hurting herself and does not meet any of the criteria above for enacting the suicide safety protocol, then we will remind patients of the resources available for counseling within the Immunology Center. We will also give everyone a list of local agencies that provide counseling services, and say: *“You may find it helpful to contact one of these agencies to set up an appointment to talk to someone about the feelings that were raised today. Also, if you are ever in crisis or need to talk to someone immediately, you can call the Immunology Center.”*

If participant has had thoughts of hurting herself or meets any of the above criteria for enacting the suicide safety protocol, then we will start suicide safety protocol, described next.

Script to Screen for Suicidal Concerns

If suicidal thoughts or severe distress are reported at screening or during any intervention or assessment session, the PD or Instructor will start the suicide safety protocol.

The PD and Instructors will be trained to use the following script. If indicated (as outlined earlier), they will ask:

“I’d like to ask you a few additional questions, because I am concerned for your well-being and safety.

1. Have you ever attempted to harm yourself in the past?	NO	YES
2. Have you thought about how you might actually hurt yourself?	NO	YES → [How? _____]

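### The plan does not settle who makes the monthly pill-count calls, and section 7.6 gives that caller no blinding status

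*Combined protocol and SAP*

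**What the plan says.** **Who calls.** Section 4.2(b) states: "Assessors will have access to participant identifiers in order to call the participants for their monthly pill counts". The same paragraph treats the PD and the assessors as different people: "The only individuals who will have access to participants' identifiers will be the PD, assessors, mindfulness instructors, and health educators". Section 13.3 states: "All phone contacts with the participants will take place in a private, locked office and will be conducted by the PD". Section 8 adds: "The PD will be responsible for data collection; see section 7.6 for blinding consideration". Appendix 3 tells the participant: "A pill counter will call you several times during the study to talk to you for the study". It refers throughout to a pill counter or interviewer and never ties that role to the PD or to the assessors.

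**Who is blinded.** Section 7.6 lists as blinded the principal and co-investigators, the data management and analysis staff, and (to outcomes only) the instructors. The PD is the only person listed as not blinded: "Blinding the PD would be impractical given that she will be randomizing the patients to either condition". The impact is called minimal because participants complete the surveys electronically and the PD takes no part in analysis. Assessors and pill counters appear in neither list.

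**Suicide protocol.** One trigger in Appendix 5 is that a participant "reports suicidal thoughts at any time to PD or Instructor", and only those two roles are named as trained on the script and as starting the protocol. The Appendix 3 training outline says: "Mention that the caller will also ask some questions about how the participant has been feeling and related issues". Section 11.2 tells staff to contact an investigator at once if a participant threatens self-harm, and Appendix 3 sends life-in-jeopardy cases to project management.

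**The concern.** The phone pill count is the plan's objective measure of ART adherence. Section 2.2 faults the only earlier study of mindfulness and ART adherence partly for relying on self-report. Section 12.3 expects no change in viral load by follow-up. That leaves the pill count as the one adherence measure that is not self-reported and is still expected to respond.

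The count is not a mechanical reading. Under Appendix 3 the caller decides how hard to look for further bottles, whether a refill has occurred since the last call, when a regimen changed, and whether a visit is coded as a count or as no count. A caller who knows the arm could make these decisions differently by arm without intending to. Appendix 3 itself recognises caller influence, since it bars callers from praising or advising participants on adherence.

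Section 11.5 counts breaking the blind as a major violation. For a role with no stated blinding status, nobody can tell whether that has happened.

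**Working it through.** No sample size, power or error rate is involved. The check compares passages and counts calls.

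**1. Who is the caller?**

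| Source | Caller | Specific to pill counts? |
|---|---|---|
| 4.2(b) | Assessors, separate from the PD | Yes |
| 13.3 | PD, for all phone contacts | No |
| 8 (overview) | PD, for data collection | No; it follows a statement that assessments are in person |
| 5.2 | Not named; monthly phone counts listed as additional | Yes |
| Appendix 3 | Pill counter or interviewer | Yes |

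The only text that is both specific to pill counts and names a study role points to the assessors. The general texts point to the PD. Nothing reconciles them.

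**2. Does 7.6 cover either answer?**

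- *PD calls.* The caller knows every allocation. The two reasons in 7.6 (self-completed electronic surveys, no role in analysis) do not apply to a number obtained by a caller over the phone.
- *Assessors call.* Blinding is possible but is not stated. Two routes to the allocation are left open. The specimen adverse event record in section 4.6 names the mindfulness condition in its comments field, and Appendix 3 has the caller remind participants of upcoming intervention sessions.

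The blinding status of the objective adherence measure is therefore undefined on either reading.

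**3. How many calls are exposed?**

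Inputs: seven paid calls and two pill counts within baseline procedures (6.3); randomisation after all baseline assessments (6.2); 50 participants (5.1).

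- Check on the seven: 40 + 40 + 50 + 7 × 10 = 200 dollars, which agrees with the total in 6.3.
- Calls after randomisation: 7 − 2 = 5 per participant.
- With full enrolment and completion: 5 × 50 = 250 of 7 × 50 = 350 calls.
- If one of the two baseline counts is the in-person practice count (an assumption; the text does not say), 6 calls follow randomisation, or 6 × 50 = 300.

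**4. Appendix 5 against the other texts.**

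If the PD calls, the caller is a role named in Appendix 5. If assessors call, the role is not named there, and their instructions come from 11.2 and Appendix 3, whose triggers are worded differently. No text says how an assessor on a call hands over to the PD or an Instructor.

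**The case against.** **The contradiction may be only apparent.** The 13.3 sentence cannot literally cover every call, because instructors phone participants weekly (4.2, 7.3). It stands directly before text on interested individuals being scheduled for screening, so it reads as recruitment wording. Section 4.2 is specific, and Appendix 3 has callers take problems to project managers, which suggests someone other than the PD. This stands in large part. A reader might infer that the plan has an unblinded PD collecting the outcome; the documents do not support that as a settled fact, and assessors are the more natural reading. But the objection does not supply the missing blinding status.

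**The damage could be made to look larger than it is.** A reader might reason that one missed 30-tablet bottle shifts a once-daily 30-day figure by up to 100 points, and so the mean of an arm of 25 by 100/25 = 4 points. That is a ceiling for one participant in one interval. If five counts were averaged (an assumption), it would be 4/5 = 0.8. Appendix 3 also guards against it with double counts aloud, prescription-date checks and a comparison with the prior count and the amount dispensed. Nothing links such an error to arm, so the figure describes measurement error and not bias.

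**Adherence is not the main outcome.** Sections 3 and 7.1 list adherence and sexual risk together as secondary outcomes without ranking them, and 12.2 calls any formal testing exploratory. This stands.

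**Callers are not without safety cover.** A reader might infer that a disclosure on a pill-count call falls outside any protocol. Appendix 5 opens by applying to any patient at any time and extends to assessment sessions, and 11.2 and Appendix 3 give further routes. The call items reproduced in Appendix 3 contain no mood question, and the full booklet is not reproduced, so what callers actually ask cannot be established. What remains is a mismatch of named roles and routes.

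**Conclusion.** The point holds in limited form. The plan does not consistently identify the pill-count caller, and section 7.6 gives that role no blinding status. Its reassurance about the PD does not extend to a count that needs caller judgement. About 5 of 7 calls per participant are affected, or 6 of 7 if one baseline count is the practice count.

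The consequence falls on the exploratory estimate of the adherence effect, which section 12.6 will use to gauge whether the results are encouraging. The primary feasibility and acceptability criteria are untouched. No direction or size of bias can be stated from the documents. The change is still worth making, because it protects the plan's only objective behavioural measure of adherence at little cost.

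The mismatch between Appendix 5, Appendix 3 and section 11.2 is a separate internal inconsistency. It supports a request to reconcile them, and no view on what the rule should be.

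**What to change.** 1. Reconcile sections 4.2, 8 and 13.3 by naming the assessors already in the protocol as the pill-count callers, and use the same role name in Appendix 3. If the 13.3 sentence is meant for recruitment contacts, say so.
2. List the assessors in 7.6 as blinded to condition, with no access to the allocation table or the adverse event log, and state that the PD does not perform counts after randomisation.
3. If the PD must make these calls, state in 7.6 that pill-count adherence is collected unblinded, so that the estimate is read accordingly.
4. Reconcile Appendix 5 with Appendix 3 and section 11.2 on how the pill-count caller's role relates to the suicide protocol. The content of that rule is for the sponsor.

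The cost is wording, brief training and some scheduling constraint. This assumes that the assessors are people other than the PD and are available in sufficient number; the documents do not give their number. Caller blinding will be imperfect in any case, because participants know their condition and may mention it.

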13.4. Study Discontinuation

The study may be discontinued by the IRB, the NCCIH, the OHRP, the FDA, or other government agencies as part of their duties to ensure that research participants are protected.

13.5. Unanticipated Problems

The Office for Human Research Protections (OHRP) considers unanticipated problems involving risks to participants or others to include, in general, any incident, experience, or outcome that meets **all** of the following criteria:

- Unexpected (in terms of nature, severity, or frequency) given (a) the research procedures that are described in the protocol-related documents, such as the IRB-approved research protocol and informed consent document; and (b) the characteristics of the participant population being studied;
- Related or possibly related to participation in the research (in the guidance document, possibly related means there is a reasonable possibility that the incident, experience, or outcome may have been caused by the procedures involved in the research); and
- Suggests that the research places participants or others at a greater risk of harm (including physical, psychological, economic, or social harm) than was previously known or recognized.

An incident, experience, or outcome that meets the three criteria above generally will warrant consideration of substantive changes in order to protect the safety, welfare, or rights of participants or others.

Procedures for handling the reporting of adverse events and serious adverse events to the Institutional Review Board at The Miriam Hospital, NCCIH and the Data Safety and Monitoring Committee are detailed in the DSM plan and in section 4.4 of this protocol.

APPENDICES

DESCRIPTION

- 1 Protocol for Mindfulness Training
- 2 Protocol for Health Coaching
- 3 Protocol for Telephone-Based Pill Count
- 4 Qualitative Interview Guide
- 5 Suicide Protocol

References

1. Centers for Disease Control and Prevention. Estimated HIV incidence among adults and adolescents in the United States, 2007–2010. *HIV Surveillance Supplemental Report* 2012; 2012;17.
4. Centers for Disease Control and Prevention. Monitoring selected national HIV prevention and care objectives by using HIV surveillance data—United States and 6 dependent areas—2012. Atlanta, GA2014 Published November 2014.
5. Centers for Disease Control and Prevention. *HIV Surveillance Report*, 2012 Published November 2014.
